## 1.0 INTRODUCTION

On 17 Nov 2006, the U.S. Food and Drug Administration (FDA) approved Mentor's MemoryGel® silicone gel-filled breast implants for use in women who are undergoing primary or revisional breast augmentation and primary or revisional breast reconstruction surgery. The approval was conditional on Mentor conducting a 10-year study designed to collect long-term experience in U.S. women with MemoryGel implants. The MemoryGel Postapproval Study (MemoryGel PAS) is intended to satisfy one element of FDA's postapproval requirements.

As a condition to gaining access to MemoryGel products, physicians were required to sign up for the MemoryGel Gel-Filled Breast implants Post Approval study, and were asked to actively encourage 41,900 women to participate in the 10-year study. In addition, the study included 1,000 women who were undergoing breast implantation with saline breast implants to serve as concurrent controls for assessing rheumatologic and neurologic signs and symptoms.

Approximately 1,700 centers participated in the study and enrollment included 41,451 MemoryGel participants and 1039 saline participants. Study enrollment has been closed since 15 Oct 2008. As of the last annual study report (dated Nov 2013), the follow-up rates through six years were 21.8% for MemoryGel participants and 15.0% for saline participants.

Due in part to the low follow-up rate, which may limit interpretation of the data, FDA in collaboration with the American Society of Plastic Surgeons (ASPS), breast implant manufacturers, and patient representatives have been investigating innovative approaches to collect long-term data on silicone gel breast implants. As part of these efforts, recently, FDA has agreed to changes in the postapproval commitments for the MemoryGel silicone gel-filled breast implants that include changes to MemoryGel PAS. These changes are described in this amended protocol.

This amended protocol limits the scope of data collection under the original protocol to the collection of only secondary procedure/reoperation data. There are no longer requirements for scheduled office visits or annual participant questionnaires, which included the collection of data on conditions and diseases such as connective tissue disease, rheumatological signs and symptoms, and neurological disease. The limited data collected under this protocol amendment are similar in scope to the data collection planned for the National Breast Implant Registry, and therefore, this amended protocol will serve as a pilot for the future registry efforts.

## 2.0 OBJECTIVES

This amended protocol will collect data on secondary procedures/reoperations. The issues to be addressed include the following:

- What are the Kaplan-Meier (KM) implant removal and reoperation rates over time?
- What are the reasons for reoperation over time?

The postapproval study was originally designed to address the issues identified in Table 1, which includes reoperation data as described above.

**Table 1. ORIGINAL POSTAPPROVAL STUDY OBJECTIVES**

Complication/ Condition/ Disease	Issues to be Addressed
Local Complications	
 
• What are the Kaplan-Meier (KM) complication rates over time, including removal and reoperation rates?
 
• What are the reasons for reoperation over time?
 

Connective Tissue Disease (CTD)	
 
• What are the types and rates of CTD diseases reported for women receiving Mentor MemoryGel implants and controls?
 

Rheumatological Signs and Symptoms	
 
• What are the types and rates of rheumatological signs and symptoms reported for women receiving Mentor MemoryGel implants and controls?
 

Neurological Disease	
 
• What are the types and rates of neurological diseases reported for women receiving Mentor MemoryGel implants and controls?
 

Neurological Signs and Symptoms	
 
• What are the types and rates of neurological signs and symptoms reported for women receiving Mentor MemoryGel implants and control group?
 

Offspring	
 
• What are the rates of birth defects/congenital malformations (such as cleft lip, cleft palate, neural tube defect, esophageal deformity, and pyloric stenosis), premature birth, low birth weight, neonatal intensive care, and chronic illnesses (such as autoimmune disorders, cancer, and neurological disease) in children born to women receiving Mentor MemoryGel implants and controls?
 

Reproductive	
 
• Of those women who attempted to have children, what are the rates of miscarriage and stillbirths for women receiving Mentor MemoryGel implants and controls?
 

Lactation	
 
• Of those women who attempted to breast feed, how many were able in each of the groups (women receiving Mentor MemoryGel implants and controls)? What are the types and rates of lactation problems for women receiving Mentor MemoryGel implants and controls?
 

Cancer	
 
• What are the types and rates of cancer reported for women receiving Mentor MemoryGel implants and controls?
 

Suicide	
 
• What are the rates of suicide for women receiving Mentor MemoryGel implants and controls?
 

Mammography	
 
• What is the rate of rupture with mammography in women receiving Mentor MemoryGel implants?
 
• Are there interference issues (i.e., is there an effect with respect to the timing of breast cancer diagnosis?)
 

MRI Compliance and Results	
 
• How many women receiving Mentor MemoryGel implants obtained MRIs as described in the patient brochure (i.e., at year 3 and every 2 years, thereafter)? If not this schedule, how often did they get one?
 
• What are the rupture rates based on the MRI findings?
 

 To include (patient-reported key local complications): infection; breast pain; capsular contracture (Baker Grades I-IV); rupture; removal; and reoperation. Physicians will

report all local complications, including reasons for reoperation, with or without removal, and reasons for removal, during scheduled and unscheduled/interim visits (see complications form in Section 15).

-  To include the following diseases diagnosed or reviewed and confirmed by a board-certified rheumatologist; scleroderma, lupus, rheumatoid arthritis, Sjögren's Disease, fibromyalgia, and other CTDs or autoimmune diseases [participant to specify in questionnaire]. Separately, a survey-based evaluation of fibromyalgia, determined through patient reports via a validated instrument that correlates to rheumatologist diagnosis, will be included (Katz, R.S., F. Wolfe and K. Michaud. 2006. Fibromyalgia diagnosis: a comparison of clinical, survey, and American College of Rheumatology criteria. *Arthritis Rheum.* 54(1):169-176).
-  To include: persistent joint stiffness that lasts at least one hour, over a period of two weeks or longer; persistent non-traumatic joint pain (more than 3 months); persistent joint swelling (more than 1 week); persistent muscle pain (more than 3 months); pain in taking a deep breath for more than a few days (pleurisy); persistent sleep disorders at night; persistent fatigue; persistent cognitive problems; frequent muscle cramps; persistent skin redness on both cheeks; loss of weight without dieting; skin that persistently feels tight, stretched, or hidebound; skin that breaks out routinely after being in the sun, other than sunburn; fingers becoming unusually pale, numb, or uncomfortable in the cold; excessively dry eyes or mouth; persistent unexplained fevers; ulcers in mouth for more than 3 weeks; difficulty swallowing; and unusual hair loss.
-  To include the following diseases diagnosed or reviewed and confirmed by a board-certified neurologist: multiple sclerosis (MS); myositis (polymyositis, dermatomyositis, inclusion body myositis); and other neurological diseases [participant to specify in questionnaire].
-  To include: persistent or recurrent tingling or numbness with a duration of at least several weeks; episode of sudden visual loss or double vision; persistent or recurrent dizziness; persistent memory problems, difficulty concentrating on simple tasks, such as reading, television, etc., lasting at least 3 months; difficulty with balance; new difficulty walking that is not related to arthritis; persistent muscle weakness with a duration of at least several weeks; loss of control of bowel or bladder that happens suddenly or urine retention; jaw weakness leading to difficulty chewing; and seizure, convulsion, or fit.
-  Cancers: breast, lung, brain, and other cancers [participant to specify in questionnaire].
-  Suicide information will be obtained from relevant sources, including the Social Security Death Index and designated contacts.

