## STUDY EVALUATIONS

This protocol amendment includes the following evaluations:

Evaluation	Evaluator
Unscheduled/interim reporting of secondary procedures/reoperations*	Surgeon
*MemoryGel participants only	

Surgeon evaluations are being done to record reoperation procedure information and reasons for reoperation, with or without removal, for the MemoryGel participants only. These data were also recorded under the original protocol. A flow chart of the postapproval study process is depicted in Figures 1 and 2 (gray highlights show completed actions). All data will be forwarded to a third party study entity that will be responsible for administering the study database and analyzing the study data.

The postapproval study originally included the following evaluations:

[figure not shown]
Evaluation	Evaluator
Baseline questionnaire (preoperative)	Participant
Operative procedure	Surgeon
Follow-up questionnaire annually, 1-10 years	Participant
Unscheduled/interim reporting of key local complications and results of MRI evaluations	Participant*
Unscheduled/interim reporting of results from rheumatological or neurological referral evaluations	Participant
1 visit in Year 1	Surgeon*
1 visit in Years 4-6	Surgeon*
1 visit in Years 9-10	Surgeon*
Unscheduled/Interim visits	Surgeon*
Questionnaire at time of any participant discontinuation (when possible)	Participant**

\*MemoryGel participants only

[figure not shown]
\*\*In addition, the third party study entity will complete a Discontinuation Form documenting the date and reasons for discontinuation

Surgeon evaluations are being done to record all local complications (including reasons for reoperation, with or without removal, and reasons for removal) for the MemoryGel participants only. Because of the mobility and general good health of participants who will be receiving MemoryGel implants, Mentor will encourage the appropriate medical societies to host Internet-available listings of surgeons who are available to perform follow-up evaluations of any MemoryGel participant in the postapproval study. A flow chart of the postapproval study process is depicted in Figures 1 and 2. All participant and surgeon data will be forwarded to a third party study entity that will be responsible for administering the study database and analyzing the study data

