## **7.0 MEDICAL DEVICE REPORTING**

On a routine basis, the third party entity will report to Mentor pre-specified events (e.g., death of a participant) involving MemoryGel and Mentor saline breast implants consistent with Medical Device Reporting (MDR) standards. All data, including MDR-reported data, will be part of the annual reports for the MemoryGel™ PAS.

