## **10.0 MEDICAL RECORDS**

The postapproval study was originally designed to address the issues identified in [Table 1 and](#), in certain circumstances (see protocol Amendment 1), medical records of MemoryGel participants were to be obtained to confirm information provided by the participant. Medical records will be not obtained under this amended protocol.

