#### **CTDs, Fibromyalgia, Cancer, Neurological Diseases and Suicide**

*The incidence of CTDs (by type), fibromyalgia, cancer (by type), neurological disease (by type), and suicide will each be estimated as the ratio of the number of new cases to the number of person-years of exposure (i.e., observed person-years with silicone breast implants) for MemoryGel participants only. Ninety-five percent confidence intervals will be computed. For CTDs, the incidences of scleroderma, lupus, rheumatoid arthritis, Sjögren's Disease, fibromyalgia, and other CTDs will each be estimated. For cancer, the incidences of breast, brain, lung, and other cancers will each be estimated. For neurological diseases, the incidences of MS, myositis, and other neurological diseases will each be*

*estimated. In addition, Mentor will examine the prevalence of depression and anxiety. Ninety-five percent confidence intervals will be computed.*

*The relative risk for women with MemoryGel implants as compared to national norms will be estimated, standardizing for age, race, and other relevant characteristics, when appropriate. The relative risk will be tested for significance based on a one-sided test conducted at the 0.05 level of significance. Ninety-five percent confidence intervals will also be computed. The sources for the comparison data will include Mayes et al. (2003), and may also include, as appropriate, relevant historical controls such as Brinton et al. (2000, 2001a and b, 2004, and 2006), Hennekens et al. (1996), Deapen et al. 1997, Surveillance Epidemiology and End Results (SEER), National Violent Death Reporting System, U.S. Census data (2002), and/or other reliable and relevant sources, including new sources that may become available during the course of this study. The sources for the comparison data for fibromyalgia will include Brinton et al. 2004, the saline control participants, and/or other reliable and relevant sources, including new sources that may become available during the course of this study.*

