 Death, cause of Death: _____													
 Other, specify: _____													
Principal Investigator's Signature	Date: 
 
  	 	 	
 
 DD                      MMM                      YYYY												
Principal Investigator's Printed Name													
V1 - 14JAN2015	Confidential CRF	Discontinuation

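### By the stated definition, cancer cases for the Amendment 1 report come from annual participant questionnaires, so women who die before the next one are missed and the relative risk against a registry-type norm is biased downward

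*Combined protocol and SAP*

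**What the plan says.** Amendment 2 stops the questionnaires (Section 1.0). Section 11.1 nevertheless requires a final report on all data up to the end of the Amendment 1 phase, analysed as in the original protocol. The cancer analysis is part of that report.

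- **Case source.** Table 1, footnote 6: "Cancers: breast, lung, brain, and other cancers [participant to specify in questionnaire". Section 5.0, Study Evaluations, lists "Follow-up questionnaire annually, 1-10 years" with the participant as evaluator. Under the original design, surgeon visits record local complications. Interim participant reports cover local complications, MRI results and rheumatological or neurological referrals.
- **Medical records.** Section 10.0 gives their purpose: "medical records of MemoryGel participants were to be obtained to confirm information provided by the participant". They check reports and are not described as a way to find unreported cases.
- **Contrast with suicide.** Table 1, footnote 7: "Suicide information will be obtained from relevant sources, including the Social Security Death Index and designated contacts". Cancer has no equivalent statement.
- **Death and discontinuation information.** Section 5.0 says "the third party study entity will complete a Discontinuation Form documenting the date and reasons for discontinuation". In Section 7.0, "the third party entity will report to Mentor pre-specified events (e.g., death of a participant" under device reporting. The Amendment 2 Discontinuation Form (Section 16.0) has an entry for "Death, cause of Death". None of these is tied to cancer incidence.
- **Analysis.** Section 11.1: "For cancer, the incidences of breast, brain, lung, and other cancers will each be estimated". Incidence is new cases over observed person-years. The relative risk against national norms is tested one-sided at 0.05. Possible sources for the norms (Table 2, footnote 6) include the SEER cancer registry programme, published implant cohorts and others.

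**The concern.** When only the participant can report a cancer, a cancer that kills her before her next questionnaire produces no report. The diagnosis itself causes the missing data. Her earlier person-time stays in the denominator while her case never enters the numerator. A norm built from a registry that counts cases regardless of survival has no such gap, so the two sides of the ratio are measured differently.

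The error runs toward reassurance. The test looks for excess risk in one direction, and missed cases pull the estimate down and cost power. The shortfall grows with the speed at which a cancer kills, so it differs between the sites that the plan will estimate separately. A reassuring result for a rapidly fatal cancer could partly reflect women who did not live to answer.

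This is distinct from the low follow-up that Section 1.0 acknowledges (21.8% through six years). Drop-out unrelated to disease removes later person-time together with later cases. The loss described here would remain even if every surviving, able woman responded.

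**Working it through.** **1. The plan's own figure.** The documents give no figure for cancer ascertainment. The nearest is the sample size in Section 11.2: relative risk 2.0, background 2.85 per 100,000, one-sided 0.05, 80% power, about 338,000 person-years.

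- Expected events under the null: 338,000 × 2.85/100,000 = 9.633. At relative risk 2.0: 19.266.
- Exact Poisson test: reject at 16 or more events. Actual alpha is 0.037 and power 0.802.
- Person-years per participant: the sum of (1 − 0.035k) for k = 1 to 10, which is 10 − 0.035 × 55 = 8.075. Then 338,000 / 8.075 = 41,858, against 41,900 stated.

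The plan's figures reproduce.

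**2. Model for missed cases.** Assumptions: diagnoses fall evenly over the year between questionnaires; survival after diagnosis is exponential with median m years; every survivor responds and reports; the norm is complete. With L = ln 2 / m:

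- counted share = (1 − e^(−L)) / L
- missed share = 1 − counted share
- observed relative risk = 2.0 × counted share

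The documents give no survival figures, so m is shown as a range. The last column applies the 16-event rule with mean 19.266 × counted share. It borrows the planning rate, which is for scleroderma, because no cancer rate is given.

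| Assumed median survival (years) | L | Counted share | Missed share | True RR 2.0 reads | Power (80.2% if all counted) |
|---|---|---|---|---|---|
| 0.5 | 1.386 | 0.541 | 0.459 | 1.08 | 7% |
| 1 | 0.693 | 0.721 | 0.279 | 1.44 | 32% |
| 2 | 0.347 | 0.845 | 0.155 | 1.69 | 56% |
| 5 | 0.139 | 0.934 | 0.066 | 1.87 | 71% |

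**3. Same model in terms of the chance S of still being able to respond one year after diagnosis.** Here incapacity counts as well as death, and the counted share is (1 − S) / (−ln S). At S = 0.95 a true 2.0 reads 1.95; at 0.8, 1.79; at 0.4, 1.31; at 0.2, 0.99. The bias is downward for every S below 1, and small when S is near 1.

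**4. Does closing person-time at the last questionnaire repair it?** No. A missed case then removes at most about one year from some 338,000, or 0.0003%. The same case is 1/19.266, about 5%, of the expected numerator at relative risk 2.0.

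**5. Longer gaps.** Section 14.0 allowed three years without a questionnaire or surgeon form before a woman was discontinued for non-compliance. For a three-year gap the counted share is (1 − S³) / (−3 ln S). At S = 0.8 it falls from 0.90 to 0.73.

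**The case against.** - **The footnote may be overread.** Footnotes 2 and 4 use a similar bracket after their own residual categories, so in footnote 6 it may only ask the participant to name the type of other cancer. That is a fair reading of the bracket. It does not supply another source: the annual questionnaire remains the only route that the supplied text describes for cancer.
- **Amendment 1 is not supplied.** Sections 5.2, 8.0, 9.0 and 10.0 refer to it for discontinuation, survey methods and records. It may contain a rule for women who died. This limits the point to the text available, but a referral elsewhere does not show that such a rule exists.
- **Other information exists.** There are third-party death reports, discontinuation reasons, a discontinuation questionnaire when possible, and a surgeon entry for breast cancer on the Amendment 2 reoperation form. A reader might infer that cancer could be learned only from questionnaires. The documents do not go that far. What they lack is a rule carrying this information into the cancer count.
- **The norms may not be complete.** A reader might infer that the norms count every case. Table 2 and Section 11.1 offer an optional list that includes published cohorts, and say nothing about completeness for any source. The downward bias is therefore conditional on a registry-type comparator assumed to count cases regardless of survival. A cohort with similar self-report could share the gap.
- **Counting every cancer death would introduce new errors.** The cohort includes reconstruction patients whose tissue was removed because of cancer, and the estimator requires new cases. Extending person-time only for women who died would also count deaths in intervals where other non-responders contribute no time. Both objections stand and shape the fix.
- **Low follow-up is the broader problem.** This is true, and it limits the gain from any correction, but it does not remove this bias.

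**Conclusion.** The point holds in conditional form. By the stated definition, cancer cases for the Amendment 1 report come from annual participant questionnaires, and nothing supplied brings deaths into the count. Against a registry-type norm the relative risk is biased downward, and more so the faster a cancer kills. The direction follows from the design. The size does not: a true 2.0 reading 1.1 to 1.9 rests on assumed median survival of 0.5 to 5 years, evenly spread diagnoses, full response by survivors and a complete norm. The power figures also borrow a scleroderma rate.

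A reader might infer that lung and brain cancer are shown to be the worst affected. The documents give no survival by site, so only the dependence on survival can be asserted. The matter is worth settling before the Amendment 1 report is written. It does not bear on the reoperation analyses under Amendment 2.

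**What to change.** Keep the questionnaire-based analysis as primary and add one sensitivity analysis to the Amendment 1 report:

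1. Count a cancer recorded as cause of death, from whatever discontinuation, death-report or designated-contact information was collected, when death falls after a completed questionnaire and before the next was due.
2. Exclude cancers present before implantation or at baseline, and cancers already reported.
3. For this analysis, run person-time to death for women who died and to the next questionnaire due date for all other women, so that cases and person-years cover the same intervals.
4. Report the relative risks both ways. State that cancers in surviving non-responders, including women too ill to respond, remain uncounted. Present the result alongside the primary one, not as a full correction.
5. If Amendment 1 already has a rule for women who died, cite it in the report.

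The cost is a coded review of cause-of-death information plus a paragraph of analysis text. Cause of death is less specific than a registry diagnosis. Its availability must also be checked first: the cause-of-death field is visible only on the Amendment 2 form, and the earlier form is described only as giving date and reasons.

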## 11.2 Sample Size Determination

Study enrollment has been closed since 15 Oct 2008 and no new study participants will be enrolled.

The sample size for the postapproval study originally was determined in the following manner:

*It is assumed that it is required to have 80% power to be able to detect as statistically significant a relative risk of 2.0 for adverse events that occur, without implants, with a frequency of 2.85 per 100,000. This figure is based on the incidence of scleroderma as reported by Mayes et al. (2003). It is assumed this would be based on a one-sided test conducted at the  $\alpha = 0.05$  level of significance. Based on these specifications, it was determined that approximately 338,000 person-years would be required.*

*Patients are to be followed for 10 years. For purposes of sample size calculation, assuming a follow-up rate of 65% at 10 years and a linear loss to follow-up, there would be an average of 8.075 person-years per participant. Thus, in order to obtain the 338,000 person-years, a total of 41,900 MemoryGel participants would be required.*

*The concurrent control sample size was selected in order to be able to detect a relative risk of 2.0 for MemoryGel participants as compared to control participants, for rheumatologic and neurologic signs and symptoms with a prevalence of approximately 2% among MemoryGel participants. It is assumed this would be based on a one-sided test conducted at the 0.05 level of significance with a power of 80%. Similar combined rheumatologic categories of signs and symptoms from Mentor's existing Core Study of these silicone gel implants all have estimated prevalence of at least 2% after year 2. These data will be analyzed by first computing, for each participant, the proportion of time points in which the participant reports the sign or symptom as being prevalent and then calculating the mean of these participant-level proportions across participants within each group. For purposes of sample size calculation, it is assumed that these means will be compared using a simple test based on the normal approximation.*

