*Consents and releases will be broad enough to secure permission to: access medical records required to be collected by this protocol; contact individuals that the participant has designated as a means to locate the participant; use Social Security Numbers to search proprietary databases (e.g., the National Change of Address (NCOA) database, the Social Security Death Index database, and other proprietary databases) as needed. Consents and releases will also permit participant data and information to be provided to the Food and Drug Administration (FDA), Institutional Review Boards (IRBs), and/or courts as needed. Additionally, informed consents and releases will make reference to the agreement of the participant to cooperate in allowing the third party study entity to obtain medical records required by this protocol.*

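### Suicides can be found without the woman's participation, yet the rate divides them by observed person-years only, and no visible rule ties the two to the same window

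*Combined protocol and SAP*

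**What the plan says.** **Numerator.** Footnote 7 to Table 1 (Section 2.0) says: "Suicide information will be obtained from relevant sources, including the Social Security Death Index and designated contacts". Section 13.0 has the consent and release forms allow the study to "use Social Security Numbers to search proprietary databases" when the need arises, and the death index is among the databases it names. Section 15.0 repeats this.

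**Denominator.** In Section 11.1, one paragraph covers connective tissue disease, fibromyalgia, cancer, neurological disease and suicide. For each, the incidence is new cases divided by person-years of exposure, explained as "observed person-years with silicone breast implants". Suicide has no definition of its own.

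**Test.** The same part of Section 11.1 compares the rate with national norms: "The relative risk will be tested for significance based on a one-sided test conducted at the 0.05 level of significance".

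**Follow-up achieved.** Section 1.0 reports that "the follow-up rates through six years were 21.8% for MemoryGel participants and 15.0% for saline participants". MemoryGel enrollment was 41,451.

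**Where it still applies.** Amendment 2 collects reoperation data only. Section 11.1 still calls for a final report on the Amendment 1 phase, from the start of the study, using the analyses of the original protocol. The suicide analysis belongs to that report.

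**The concern.** For a disease reported by questionnaire, a woman who stops responding leaves the numerator and the denominator together. Suicide is different. A death-index search or a designated contact can reveal a death years after the woman's last response, while her person-time may have ended long before. Counting that death over observed time alone puts an event in the numerator with no matching time at risk below it. Women who also stopped responding but are alive add neither events nor time after loss, so nothing offsets the error.

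The bias is upward whenever post-loss deaths are counted, and it grows with loss to follow-up. The design assumed 65% retention at ten years; the reported figure is 21.8% through six. The result is a mortality safety outcome, tested one-sided and reported to FDA, so a mismatch could by itself produce an apparent excess.

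**Working it through.** **1. The plan's own figures.** Section 11.2 asks for "80% power to be able to detect as statistically significant a relative risk of 2.0" for an event occurring "with a frequency of 2.85 per 100,000" (scleroderma, not suicide) and arrives at 338,000 person-years.
- Expected cases under the null: 338,000 × 2.85/100,000 = 9.633. The exact one-sided Poisson test rejects at 16 or more cases (attained level 0.037). Power at relative risk 2.0 (mean 19.266) is 0.802, which agrees with the plan.
- Person-years per participant, with linear loss to 65% counted at each year end: Σ(1 − 0.035t) for t = 1 to 10 = 8.075, as stated. Continuous linear loss would give 10 × (1 + 0.65)/2 = 8.25.
- Number of women: 338,000/8.075 = 41,858, stated as 41,900.

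The year-end convention is therefore the protocol's own way of counting time.

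**2. Formula for the mismatch.** Assume that every enrolled woman is searched, every suicide is found and counted, and the hazard is the same before and after loss. Then

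overstatement = full person-years ÷ observed person-years.

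**3. At the planned retention, over ten years.** 10/8.25 = 1.21; 10/8.075 = 1.24.

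**4. At the reported follow-up, over six years.** Full time is 41,451 × 6 = 248,706 person-years. Retention S at year six is taken as 0.218.

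| Loss pattern | Observed years per woman | Overstatement | If half of post-loss suicides are found |
|---|---|---|---|
| Continuous linear | 6 × (1 + 0.218)/2 = 3.654 | 1.64 | 1.32 |
| Linear, year-end counting | Σ(1 − 0.782t/6), t = 1 to 6 = 3.263 | 1.84 | 1.42 |
| Exponential | 6 × 0.782/(−ln 0.218) = 3.080 | 1.95 | 1.47 |
| No loss until year 5, then linear | 5 + 1.218/2 = 5.609 | 1.07 | 1.03 |
| Drop at year 1, then flat | 1 + 5 × 0.218 = 2.090 | 2.87 | 1.94 |

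The last column is 1 + 0.5 × (overstatement − 1).

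**5. What this could do to the test.** The documents give no reference suicide rate. I **assume** 5 per 100,000 person-years, with a range of 2.85 to 10, and a true relative risk of 1 over six years in 41,451 women. True expected deaths are 248,706 × 5/100,000 = 12.4.
- At 1.64-fold, the analysis expects 12.4/1.64 = 7.6 deaths and rejects at 13 or more. The chance of a false finding is 0.47 (0.28 to 0.67 over the assumed rates).
- At 1.84-fold, it expects 6.8 and rejects at 12 or more. The chance is 0.59 (0.41 to 0.81).

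The nominal level is 0.05. These probabilities illustrate the conditions in step 2; they do not predict the report's result.

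**The case against.** The strongest reply is that the mismatch rests on two things the documents do not say.

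- **Who is searched.** Sections 13.0 and 15.0 allow database searches only as the need arises, alongside address databases and contacts used to locate women. That fits case-by-case tracing at least as well as a sweep of the whole cohort. A reader might infer that the index is searched for every woman lost to follow-up; no passage says so.
- **When observed time ends.** Section 11.1 does not say that it stops at the last questionnaire. Section 14.0 shows that discontinuation for non-compliance required three years with neither a questionnaire nor a surgeon's form, so participation can outlast the last response. The 21.8% is not defined either, and may be a questionnaire response rate rather than retention.

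Amendment 1, to which this document refers for follow-up and discontinuation details, is not available here and might contain a linking rule.

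All of this stands as a limit on the size. It does not remove the defect. Footnote 7 names sources that work without participation, Section 11.1 states one formula for suicide and the questionnaire diseases alike, and no visible text restricts the deaths to the observed window.

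A reader might also infer that excluding deaths after the last questionnaire would lose nearly all suicides. That is not supported: a suicide between annual contacts in an active participant falls within follow-up under any ordinary rule. Only deaths after follow-up has ended are in question.

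**Conclusion.** The suicide numerator and denominator are not tied to the same window, and if post-loss deaths are counted the rate and relative risk in the Amendment 1 final report are too high. The direction is certain on that condition; the size is not.

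Under complete search and capture, equal hazard, and 21.8% read as retention at six years, the factor is 1.64 to 1.95 for steady loss. It is 1.3 to 1.5 if half the post-loss suicides are found, and about 1.2 at the planned retention. With no loss curve documented, other shapes give 1.07 to 2.87.

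A reader might conclude that the rate is inflated almost two-fold. The documents do not support that as a headline: it needs every favorable assumption plus exponential loss, a shape they never use. Extending full time to year 7 (290,157 person-years) over six-year observed time (151,462) would give 1.92, but it credits no observed time in year 7. Holding 21.8% through year 7 gives 290,157/160,498 = 1.81; continuing the linear loss gives 290,157/157,797 = 1.84.

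The point does not touch the Amendment 2 analyses or the questionnaire-reported diseases.

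**What to change.** In the analysis text for the Amendment 1 final report, for suicide only, state the search population, the search date and the censoring rule, and use one window for deaths and person-years.

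- **If the index is searched for all consenting MemoryGel women:** count deaths and person-years from implantation to the earliest of death, known explantation or the search date.
- **Otherwise:** count only suicides dated within a defined follow-up period that ends at discontinuation rather than at the last questionnaire. The sources should then be checked over that period for every woman who contributes time to it.

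Report the other version as a sensitivity analysis where the searches allow it. Keep observed person-years for the questionnaire-reported diseases.

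The cost is mainly wording. A cohort-wide version needs a full index search if none has been done; the consent described in Section 13.0 provides for such searches. The search-date version has a downside that the report should state: explantation after loss is unknown and index capture may be incomplete, so it may include some unexposed time and understate the rate.
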